# ***In Vivo Kinematics for Subjects With Smith & Nephew Journey II BCS TKA, Journey II CR TKA, Or Journey II XR TKA***

NCT04612036

10/27/2020

[name]  
University of Tennessee  
[name]  
[name]  
[contact]  
[contact]  
Email: [[contact]](mailto:[contact])

In vivo knee kinematics will be assessed for 50 subjects that have been implanted with either a Smith & Nephew BCS, XR, or CR TKA. All TKAs should be judged clinically successful (KSS > 80). A KSS score of greater than 90 is deemed to be excellent by the Knee Society. Each subject should have a well-functioning prosthesis, be at least three months post-operative, and should have good-to-excellent post-operative passive flexion.

Deciding which patients received which kind of implant was up to the discretion of [name], according to his professional opinion. The determination as to which type of implant patients received is outside the scope of this particular study. Subjects will already have the knee implants and must be at least three months post-operative. Bilateral subjects will not be included in the study populations.

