## DATA ANALYSIS

The kinematic variables of interest included the femoral and tibial 3D rotational and translational kinematics. The relative motion of the femoral component and tibial component were calculated based on the transformation matrices of each rigid body. This information was then used to extract anterior/posterior low points and contact points as well as internal/external rotation of the femoral component with respect to the tibial component.

Once the subjects have completed the activity, the fluoroscopic videos will be stored digitally and specific frames of interest will be captured from the video and exported into the preprocessing software. The specific frames of interested will be full extension, maximum knee flexion (both inclusive), and 30° knee flexion increments during the complete flexion cycle.

Our 3D to 2D registration technique will be used to overlay the 3D models of the implanted components on their projection in the 2D fluoroscopic image. The fluoroscopic video would be digitized into frames and corrected for distortion. From here, the distortion-free images would be used with the 3D to 2D registration technique to extract in vivo patient femorotibial kinematics, which involves overlaying the 3D models of the components on their projection in the 2D fluoroscopic image.

Statistical analysis of the data will be carried out to analyze the two cohorts. All variables, except for lift-off and VAG, will be denoted as continuous. The data will be first checked for normality using the Shapiro-Wilk test. Only when the data is found to be normally distributed will parametric tests be used; otherwise, non-parametric tests will be used. The data will also be tested for equality of variance using the Barlett's test and Levene's test. The final selection criterion for the type of test to conduct will be based on the check for normality, as well as the check for equal variance. Therefore, for all the continuous variables, the following tests will be used:

1. Student's t-test (when the data is normally distributed and has equal variance).
2. Welch Anova test (when the data is normally distributed but has unequal variance).

3. Wilcoxon Mann Whitney U-test (when the data is not normally distributed).

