Lift-off, as applicable, will be treated as a categorical variable in this study and a contingency analysis using the Fisher's exact test will be carried out. All statistical tests will be carried out at 95% confidence level ( $\alpha=0.05$ ) and will be performed using JMP® Statistical DiscoveryTM (SAS Institute Inc., Cary, NC) software.

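### Implant type was chosen by professional discretion, but the analysis plans only covariate-free tests, so an implant difference cannot be separated from a difference in measured patient characteristics

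*Combined protocol and SAP*

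**What the plan says.** **Allocation.** The opening description, under the title, says "Deciding which patients received which kind of implant was up to the discretion of" one named person, exercising professional judgement. It adds: "The determination as to which type of implant patients received is outside the scope of this particular study". Implants were already in place before the study began. It names three types, "BCS, XR, or CR TKA", in 50 subjects, with no split by implant.

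**Eligibility.** Inclusion criteria set BMI below 40, age above 40, a Knee Society score of at least 80, and at least three months since surgery with no upper limit. The limits are the same for every implant.

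**Analysis.** The DATA ANALYSIS section says: "Statistical analysis of the data will be carried out to analyze the two cohorts". For continuous outcomes, "for all the continuous variables, the following tests will be used": Student's t, Welch ANOVA or Mann-Whitney. The choice among them depends on normality and equality of variance; on normality the rule is "Only when the data is found to be normally distributed will parametric tests be used; otherwise, non-parametric tests will be used". For lift-off, a "contingency analysis using the Fisher's exact test will be carried out". "All statistical tests will be carried out at 95% confidence level", that is, alpha 0.05.

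The section contains no covariate, stratum, matching, table of characteristics by implant, or caveat about non-random allocation.

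**The concern.** When a surgeon or other expert chooses the implant, the choice may follow features of the patient. If one of those features also affects knee kinematics, an unadjusted comparison mixes the two. None of the four planned tests can separate them, and no planned table would let a reader judge how alike the groups were.

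This matters because the plan goes beyond description to hypothesis tests between cohorts, and its BENEFITS section looks ahead to implant design improvements and new surgical techniques. A significant result is likely to be read as a property of the implant.

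A practical point makes it timely. The paragraph on de-identification under Data Collection gives only age in months as an example of a retained value. If sex, BMI and time since surgery are not kept, the comparison may not be recoverable later.

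**Working it through.** **No figure in the plan is at issue.** The available text gives no effect size, standard deviation, power or group split for N = 50, so there is nothing to reproduce. The 95% confidence level and alpha 0.05 agree.

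**Step 1: what the tests can use.** Student's t, Welch and Mann-Whitney each use outcome and group only. Fisher's exact test uses lift-off and group only. The rule for choosing among the continuous tests looks at the outcome's distribution and not at patient characteristics. Eligibility limits that are identical across implants narrow the sample but do not balance it.

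**Step 2: how large the effect could be (all inputs assumed).** Suppose there is no implant effect and one characteristic has correlation *r* with the outcome and differs by *d* SD between two implants.

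- Spurious difference = *r* × *d* (in SD units).
- SE = √(1/n1 + 1/n2), which is √(1/17 + 1/16) = 0.348 or √(1/25 + 1/25) = 0.283.
- Noncentrality = *r* × *d* / SE. Rejection comes from the noncentral t with n1 + n2 − 2 degrees of freedom, two-sided 0.05.

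The split 17 vs 16 is one contrast among three groups; 25 vs 25 is two groups. Both are assumptions. For the moderate case, 0.3 × 0.5 = 0.15, and 0.15/0.348 = 0.43 or 0.15/0.283 = 0.53.

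| Case | *r*, *d* | Spurious difference | 17 vs 16 | 25 vs 25 |
|---|---|---|---|---|
| Weak | 0.2, 0.3 | 0.06 SD | 5.3% | 5.5% |
| Moderate | 0.3, 0.5 | 0.15 SD | 7.0% | 8.1% |
| Extreme | 0.5, 1.0 | 0.50 SD | 28.5% | 41.0% |

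**Step 3: whether adjustment removes it.** In 6,000-run null simulations of a linear model with four covariates, HC3 standard errors gave rejection of 3.2% to 4.8% across normal, skewed and unequal-variance outcomes. With ordinary standard errors, three groups and unequal variances, rejection was 7.8% to 8.7%, which is why a robust standard error is preferred. This control holds only for a measured confounder with a linear effect.

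**Step 4: what adjustment costs.** Assume a true difference of 0.8 SD and covariates that explain none of the outcome variance. Unadjusted power comes from the noncentral t: 0.8/0.348 = 2.30 with 31 df, and 0.8/0.283 = 2.83 with 48 df. Power of the HC3 model comes from simulation.

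| Analysis | 17/16/17, one contrast | 25/25 |
|---|---|---|
| Unadjusted t-test | 0.60 | 0.79 |
| HC3 model, covariates balanced | about 0.51 | about 0.72 |
| HC3 model, one covariate imbalanced by 0.8-1.0 SD | about 0.45-0.48 | about 0.61-0.63 |

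The zero-variance-explained assumption is unfavourable to adjustment; covariates that predict the outcome would recover some or all of the loss.

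**The case against.** The strongest case against is that the harm is hypothetical. Every input in the rejection-rate illustration is assumed, the weak case is practically nominal, and the large figures need a strong correlation and a full-SD imbalance together. Nothing in the documents links age, sex, BMI or time since surgery to implant choice or to kinematics. The plan discloses the discretionary allocation openly and makes no explicit causal claim. The documented source of non-comparability, one person's judgement, would remain largely unadjusted. All of this stands, and it limits the weight of the point. It does not remove it: disclosing the allocation does not tell a reader whether the groups were alike.

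Two objections bear on the remedy and also stand. First, adjustment with HC3 in groups this small costs noticeable power, so the adjusted model should be supportive. Second, kinematics are read at several flexion increments, so modelling every one would multiply estimates; the model should be confined to the main outcomes.

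A reader might infer that the comparison is in fact biased, or that its type I error is inflated to 28-41%. The documents support neither, because they give no data by implant. A reader might also infer that nothing was done to balance the groups. Text between the Exclusion criteria and Data Collection, and within the confidentiality section, was not available for review, so matching at recruitment can be neither confirmed nor ruled out.

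**Conclusion.** The point holds as a limit on interpretation. With discretionary allocation and only covariate-free tests, the results as planned will not distinguish an implant effect from measured patient differences. Whether that distinction matters here depends on imbalances that the documents do not describe; the inflation could be negligible or substantial. The planned tests are not invalid as unadjusted comparisons. What is missing is an adjusted estimate beside them and the information needed to read them. This is a cheap improvement and not a fatal flaw. The conclusion rests on the available text, and the illustration rests on assumed correlations, imbalances and group sizes.

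**What to change.** 1. Reconcile the two cohorts in DATA ANALYSIS with the three implants in the opening description, so that the implant term is defined. If three groups are meant, Student's t and Mann-Whitney cannot serve as the overall comparison, and the tests themselves may need changing.
2. Keep unadjusted comparisons. For each main continuous outcome, which the plan should name, add one prespecified supportive linear model with implant, age, sex, BMI and months since surgery. Leave out the post-operative Knee Society score, which the implant may affect. Use a standard error robust to unequal variance, such as HC3.
3. Report unadjusted and adjusted differences side by side with 95% confidence intervals. Rank-based models are not needed, nor is a rule about disagreement that has no stated threshold.
4. Report the four characteristics by implant. Keep Fisher's exact test for lift-off, labelled unadjusted.
5. Word results as associations in a non-randomised comparison, and say that unmeasured reasons for implant choice remain.
6. If subjects were matched at recruitment, say so and reflect it in the analysis.

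**Cost.** Some wording, one table and a few models. Sex, BMI and months since surgery must be kept in the de-identified data; BMI and time since surgery are already checked at eligibility, but the plan should state that all three are recorded. If the named software does not provide the chosen standard error, another package must be named. The loss of precision falls on the added estimate only; the planned tests do not bear it.

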## Inclusion criteria:

1. Subjects will have required type of TKA.
2. Patients must be at least three months post-operative.
3. Participants must be judged clinically successful with their most recent new Knee Society score equal to or greater than 80.
4. Weigh < 250
5. BMI < 40
6. Must be >40 years of age
7. Participants must be able to perform the required activities without concern.
8. Patients must be willing to sign the Informed Consent (IC) form to participate in the study.

## Exclusion criteria:

1. Pregnant, potentially pregnant, lactating females or of childbearing age. To satisfy radiation protocol, each female subject will be asked if she is pregnant, or possibly could be pregnant. A pregnant person will not be allowed to participate in the study.
2. Subjects without the required type of knee implant.
3. Cannot not have pain in other parts of the body that would prohibit the patient from performing the activities
4. Cannot have ligamentous pain and/or laxity.
5. Unwilling to sign IC form.

6. Does not speak English.

### **Data Collection**

University of Tennessee researchers with experience conducting fluoroscopic research studies, as well as either a PI or Co-PI for the study, and possibly [name] staff will be present during the fluoroscopy procedure to walk subjects through the activities. A radiation technician (RT) employed by Parkwest Medical Center will collect fluoroscopic video while subjects perform the following activities: deep knee bend. For the DKB activity, the subjects were instructed to begin at full extension on a raised platform and take a step back while flexing their knee as far as they could, in order to obtain a maximum flexion value for each subject. For this activity, images were taken at 30° increments from full extension (0°) to maximum flexion (MAX) for the entire flexion/extension cycle. Patients were examined while performing these activities using a C-Arm type fluoroscopic unit. The fluoroscopic videos were captured digitally and transferred to a secure lab network for subsequent analysis.

If a subject does not meet the inclusion criteria, s/he will not be tested. If the participant still meets all study criteria, s/he will be asked to practice the activities to ensure s/he can comfortably complete them and experience no pain with the hospital fluoroscopy machine off (no radiation). The practice portion of the data collection without radiation will not be video-recorded. During the fluoroscopy procedure, the RT will follow the motion of the implanted knee with the fluoroscopy machine; only the knee joint (from the fluoroscopy machine) will be recorded on the fluoroscopy footage. The participant will be allowed to rest as necessary and be instructed to stop the activity at the first sign of pain.

Multiple trials of each activity may be conducted to ensure usable images have been acquired to complete the study. Radiation time will be kept as low as reasonably achievable (ALARA) and will not exceed two minutes. The RT will start the fluoroscope just prior to the subject beginning each activity trial and will stop the fluoroscope immediately after the subject completes each activity trial to ensure that the subject is not exposed during idol periods. Fluoroscopy on-time will be recorded on each subject's IC.

The fluoroscopic footage for these activities will be stored on digital video files on a secure computer workstation, uploaded onto the secure CMR database by the UT researcher that attended data collection, where identifiable data will be removed and substituted for data that cannot identify the subject (e.g., dates of birth will be removed and replaced with number of months the individual has been alive). Subjects will be assigned study and subject-specific identifiers which is how the system will distinguish the datasets.

## DATA ANALYSIS

The kinematic variables of interest included the femoral and tibial 3D rotational and translational kinematics. The relative motion of the femoral component and tibial component were calculated based on the transformation matrices of each rigid body. This information was then used to extract anterior/posterior low points and contact points as well as internal/external rotation of the femoral component with respect to the tibial component.

Once the subjects have completed the activity, the fluoroscopic videos will be stored digitally and specific frames of interest will be captured from the video and exported into the preprocessing software. The specific frames of interested will be full extension, maximum knee flexion (both inclusive), and 30° knee flexion increments during the complete flexion cycle.

Our 3D to 2D registration technique will be used to overlay the 3D models of the implanted components on their projection in the 2D fluoroscopic image. The fluoroscopic video would be digitized into frames and corrected for distortion. From here, the distortion-free images would be used with the 3D to 2D registration technique to extract in vivo patient femorotibial kinematics, which involves overlaying the 3D models of the components on their projection in the 2D fluoroscopic image.

Statistical analysis of the data will be carried out to analyze the two cohorts. All variables, except for lift-off and VAG, will be denoted as continuous. The data will be first checked for normality using the Shapiro-Wilk test. Only when the data is found to be normally distributed will parametric tests be used; otherwise, non-parametric tests will be used. The data will also be tested for equality of variance using the Barlett's test and Levene's test. The final selection criterion for the type of test to conduct will be based on the check for normality, as well as the check for equal variance. Therefore, for all the continuous variables, the following tests will be used:

1. Student's t-test (when the data is normally distributed and has equal variance).
2. Welch Anova test (when the data is normally distributed but has unequal variance).

3. Wilcoxon Mann Whitney U-test (when the data is not normally distributed).

Lift-off, as applicable, will be treated as a categorical variable in this study and a contingency analysis using the Fisher's exact test will be carried out. All statistical tests will be carried out at 95% confidence level ( $\alpha=0.05$ ) and will be performed using JMP® Statistical DiscoveryTM (SAS Institute Inc., Cary, NC) software.

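### Three implants are enrolled, but the analysis is written for two unnamed cohorts, and two of its three tests for continuous outcomes cannot compare three groups

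*Combined protocol and SAP*

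**What the plan says.** The title names three devices, "Journey II BCS TKA, Journey II CR TKA, Or Journey II XR TKA". The opening section repeats this: the 50 subjects are those "implanted with either a Smith & Nephew BCS, XR, or CR TKA". It gives no number per implant, and the surgeon's choice of implant is declared outside the study's scope.

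DATA ANALYSIS states: "Statistical analysis of the data will be carried out to analyze the two cohorts". The cohorts are not identified. For continuous variables, Shapiro-Wilk, Bartlett and Levene checks then select one of three tests:

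- Student's t-test, if normal with equal variances;
- Welch ANOVA, if normal with unequal variances;
- the Wilcoxon Mann-Whitney U-test, if not normal.

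For the categorical outcome, "Lift-off, as applicable, will be treated as a categorical variable in this study and a contingency analysis" by Fisher's exact test is planned. On error control the plan says only "All statistical tests will be carried out at 95% confidence level", with alpha = 0.05. It mentions no one-way ANOVA, Kruskal-Wallis test, list of pairs or multiplicity rule.

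**The concern.** The two parts of the document disagree on how many groups exist. Replacing two by three in the sentence would not mend it, because the t-test and Mann-Whitney branches would then be invalid. Leaving it at two does not mend it either, because nobody reading the plan can tell which subjects are in which cohort.

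If the analyst starts from the three implants enrolled, the number of groups compared could change from one outcome to the next. An outcome routed to Welch ANOVA could be a three-implant comparison. One routed to the t-test or Mann-Whitney must leave out an implant, pool two, or test selected pairs. The comparison between cohorts is the only inferential analysis described, and nothing in the text fixes this choice before the data are seen.

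**Working it through.** **Step 1. Count the groups.** Title and opening section: BCS, CR, XR = 3. DATA ANALYSIS: 2, unnamed. The total of 50 comes with no effect size, SD, power or group sizes, so it cannot be re-derived and does not help identify the cohorts.

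**Step 2. Match the tests to the groups.**

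| Branch | Test | Takes three groups? |
|---|---|---|
| Normal, equal variance | Student's t | No |
| Normal, unequal variance | Welch ANOVA | Yes |
| Not normal | Mann-Whitney | No |
| Lift-off | Fisher's exact | Yes |

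Two of the three continuous branches fail for three groups.

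The remaining steps show how much the gap could matter. Group sizes and effects are assumed, and data are simulated as normal with SD 1 unless stated.

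**Step 3. How often a two-group-only branch is reached.** Split 17/17/16, 8,000 runs. Assumed rule: Shapiro-Wilk in each group at 0.05, and variances called unequal if either Levene or Bartlett gives p < 0.05.

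- Equal SDs: t-test 80.5%, Mann-Whitney 14.0%, Welch 5.4%. The two-group-only share is 80.5 + 14.0 = 94.5%. The Mann-Whitney share agrees with 1 − 0.95³ = 14.3%.
- SDs 1, 1, 1.5: 52.8%, 14.0% and 33.2%. The share is 52.8 + 14.0 = 66.8%.

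The plan does not say how to combine the two variance tests. In the unequal-SD case, requiring both to be significant raises the share to about 80%. Using a mean-centred Levene test gives 49 + 14 = 63%. With equal SDs, checking normality on pooled residuals cuts the Mann-Whitney share to about 5%.

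**Step 4. Pairwise testing with no true difference.** Three implants give three pairs. If the tests were independent, the chance of at least one false positive would be 1 − (1 − 0.05)³ = 0.143, and the upper bound is 3 × 0.05 = 0.15. Pairs share groups, so the simulated values (200,000 runs, t-tests) are lower:

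| What is tested | At least one false positive |
|---|---|
| Any single pair | 4.9–5.1% |
| Two pairs | 8.6–9.5% |
| All three, 17/17/16 | 12.2% |
| All three, 25/15/10 | 12.1% |
| Pairs only after a significant ANOVA | 5.0–5.1% |

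Three ungated Mann-Whitney tests give 12.0% (17/17/16) and 11.5% (25/15/10).

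**Step 5. Pooling two implants.** Split 17/17/16, 100,000 runs, implants labelled A, B, C.

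| True means (A, B, C) | A vs B+C | B vs A+C | C vs A+B | One-way ANOVA |
|---|---|---|---|---|
| 0, +1, 0 | 34% | 91% | 30% | 84% |
| 0, +0.6, −0.6 | 3% | 82% | 81% | 86% |

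The second row is easy to follow. The pooled mean of B and C is (17 × 0.6 − 16 × 0.6)/33 = 0.018, almost equal to A's mean of 0, so two real effects cancel. For B against A+C, the pooled mean is −(16 × 0.6)/33 = −0.291, and the contrast is 0.6 + 0.291 = 0.891 SD.

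**Step 6. Price of adjusting.** For 17 against 16 subjects at 80% power, the detectable difference is 1.007 SD at alpha 0.05. At the Bonferroni level 0.05/3 = 0.0167 it is 1.182 SD.

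**The case against.** The strongest reply is that the plan is coherent on its own terms. With two groups all four tests are valid, and Welch ANOVA on two groups is the same test as Welch's t-test. Enrolling three implants need not mean comparing three: the title and opening section speak of assessing kinematics, and no comparative hypothesis or primary endpoint is stated. On that view the fault is one group count and two missing names. Some sections were also absent from the text available for review and might define the cohorts.

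Much of this is fair. The tests are not wrong in themselves, and a two-cohort design may be intended, so the fix allows for it. The absent sections cannot be ruled out, so the point is limited to the text available. But the analysis text itself leaves the cohorts unnamed, and a two-cohort reading leaves the third implant's subjects unaccounted for.

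It is also fair that the simulations illustrate rather than estimate. The plan mentions neither pooling nor pairwise testing, the effects are assumed, and a pooled contrast tests a different hypothesis from ANOVA. The routing shares depend on a rule the plan leaves open. None of this removes the contradiction. Finally, the study is a small, single-session, non-randomised one, but that is no reason to leave its only described comparison undefined.

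**Conclusion.** The concern holds and should be corrected before analysis. The mismatch (three implants against two unnamed cohorts, with two of three continuous tests limited to two groups) follows from the text and needs no assumption.

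Its consequence depends on the choice the analyst would have to make. Each single test keeps its 5% level. The chance of at least one false positive per outcome is about 12% if all three pairs are tested without a gate, about 9% for two pairs, and about 5% if pairs follow a significant ANOVA. Pooling may do somewhat better than ANOVA (91% against 84%) or far worse (3% against 86%). Under the routing rules tried, from about 63% to 95% of outcomes would reach a test that cannot take three groups. These figures rest on assumed splits of the 50 subjects, normal data and the assumed SDs and mean differences shown.

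**What to change.** State in both the opening section and DATA ANALYSIS which implants are compared, then match the tests to that number.

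**If all three implants are compared:**

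- Name the three cohorts (BCS, CR, XR) in place of the reference to two.
- Keep the existing normality and variance checks, leading to one-way ANOVA (normal, equal variance), Welch ANOVA (normal, unequal variance) or Kruskal-Wallis (not normal).
- Apply Fisher's exact test for lift-off to the table with three implant groups.
- State how pairs are handled: either only after a significant overall test, or with an adjustment such as Tukey-Kramer, Games-Howell or Steel-Dwass, matched to the branch.

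**If two cohorts are intended:**

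- Name the implants forming each cohort.
- Say how the third implant's subjects are used, whether pooled, described only or not compared.
- Limit comparative conclusions to those cohorts. The listed tests can then stay.

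Either version costs a few lines and no new data. The gated option needs no lower per-pair level. With an adjustment, the pairwise difference detectable at 80% power (assumed 17 against 16) rises from about 1.01 SD to at most about 1.18 SD, the Bonferroni figure.

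### Letting Bartlett's and Levene's tests choose between Student's t and Welch shifts the error rate from 0.05 when groups differ in both size and spread; using Welch throughout the parametric branch removes that part of the drift, not all of it

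*Combined protocol and SAP*

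**What the plan says.** All of this is in the combined protocol and SAP. Under DATA ANALYSIS, Shapiro-Wilk comes first: "Only when the data is found to be normally distributed will parametric tests be used; otherwise, non-parametric tests will be used". Then: "The data will also be tested for equality of variance using the Barlett's test and Levene's test". The outcome of both checks picks the test, since the "type of test to conduct will be based on the check for normality, as well as the check for equal variance". The list that follows gives "Student's t-test (when the data is normally distributed and has equal variance") and "Welch Anova test (when the data is normally distributed but has unequal variance"), with Mann-Whitney for data judged non-normal.

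The same section ends by setting alpha at 0.05 for all tests. It does not say what happens when Bartlett and Levene disagree, or whether Shapiro-Wilk is run in each group or on residuals.

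The opening description of the study population gives 50 subjects across three implant designs. It leaves the choice of implant to a clinician's judgement, outside the study, and sets no number per design. The analysis section nevertheless states: "Statistical analysis of the data will be carried out to analyze the two cohorts".

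**The concern.** Student's t holds its level if the variances are equal, or nearly so if the group sizes are equal. When both differ, its standard error is wrong: too small if the smaller group is more variable, too large if the larger group is. The variance tests are there to catch this, but at these sample sizes they often miss a real difference, and Student's t is then used where it does not hold 5%. Nothing in the design prevents unequal groups. At stake is whether the declared 0.05 is what the selection rule delivers.

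**Working it through.** **The plan's own figure.** Student's t with 48 df, two-sided, equal variances, gives 0.0500, so the stated alpha is reproduced when its assumptions hold. The total of 50 comes with no effect size, SD or power, so it cannot be checked.

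**Inputs.** From the documents: alpha 0.05, 50 subjects, and the sequence of tests. Assumed: two-sided tests; 0.05 for each preliminary test; group sizes; SD ratios of 1.5 and 2; normal data with equal means. Sizes are written first/second, and the second group has the larger SD.

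**Mechanism, by hand.** Compare the true variance of the mean difference, V = s1²/n1 + s2²/n2, with what Student's t estimates on average, P = [((n1−1)s1² + (n2−1)s2²)/(n1+n2−2)] × (1/n1 + 1/n2). The rejection rate is roughly P(|Z| > 1.96·√(P/V)).

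- 35/15, SDs 1 and 1.5: V = 1/35 + 2.25/15 = 0.1786. P = [(34 + 14×2.25)/48] × 0.09524 = 0.1300. √(P/V) = 0.853, cut-off 1.672, rate about 9.4% (simulated 9.3%).
- 15/35, SDs 1 and 1.5: V = 1/15 + 2.25/35 = 0.1310. P = [(14 + 34×2.25)/48] × 0.09524 = 0.1796. √(P/V) = 1.171, cut-off 2.295, rate about 2.2% (simulated 2.3%).
- 25/25, SDs 1 and 1.5: V = P = 0.13, so no distortion to this approximation.

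**How often the variance tests miss it.** At 35/15 with SD ratio 1.5, at least one test rejects in 49% of simulated datasets and both in 36%. Student's t is therefore kept in 51% or 64%, depending on how disagreement is handled. The two tests disagree in 49 − 36 = 13%, for which the plan has no rule.

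**Full rule, simulated.** 40,000 datasets per cell (standard error about 0.1 point at 5%). Ranges cover Shapiro-Wilk per group or on residuals, and variances called unequal if either or both tests reject. Share removed = (rule − rule without the variance step)/(rule − 5%), computed within each variant.

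| Sizes | SD ratio | Plan's rule, % | Variance step dropped, % | Share of excess removed |
|---|---|---|---|---|
| 30/20 | 1.5 | 6.0–6.5 | 5.5–5.6 | 50–64% |
| 30/20 | 2 | 5.8–6.9 | 5.6–6.5 | 12–44% |
| 35/15 | 1.5 | 6.8–7.7 | 5.3–5.4 | 79–89% |
| 35/15 | 2 | 6.4–8.2 | 5.7–7.0 | 26–64% |
| 25/10 | 1.5 | 7.7–8.5 | 5.5–5.7 | 77–84% |
| 25/10 | 2 | 7.3–9.2 | 5.9–6.7 | 49–75% |
| 40/10 | 1.5 | 8.5–9.6 | 5.7 | 82–85% |
| 40/10 | 2 | 8.0–10.4 | 6.0–7.2 | 49–76% |

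Two shares worked out: 30/20, ratio 2, residuals, either test: (6.70 − 6.50)/(6.70 − 5) = 12%. 35/15, ratio 1.5, per group, both tests: (7.45 − 5.27)/(7.45 − 5) = 89%.

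**Other configurations under the plan's rule.**

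- Larger group more variable: 4.5 to 5.2% at 20/30, 3.7 to 4.7% at 15/35, 3.0 to 4.3% at 10/40.
- Near-equal groups (25/25, 17/16): 5.3 to 6.2% with unequal SDs, 5.0 to 5.1% with equal SDs.
- Unequal sizes, equal SDs: 5.1 to 5.5%.

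An independent simulation agrees: with Shapiro-Wilk per group, 35/15 at ratio 1.5 gave 7.0 to 7.6%, falling to 5.4% without the variance step. It also shows that the drift due to the variance step is greatest at moderate ratios. At ratio 3 and 35/15 the variance tests almost always reject, and the rule gives 6.5 to 6.6% against 6.5% without the step.

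**The case against.** The strongest reply is that the premise is hypothetical. The documents make unequal groups possible, not likely, and say nothing about SDs. One imbalance alone does little harm; at 20/30 the rule is near nominal, and 30/20 (5.8 to 6.9%) overlaps the near-equal cells (5.3 to 6.2%). The largest figures need 40/10, the most extreme split tried. This stands: the figures are conditional, and nobody can say from the documents that this trial's error rate is inflated, or in which direction.

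Four stronger readings are tempting and do not hold.

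- A reader might infer that moving to Welch restores 5%. Welch with no normality check gives 4.8 to 5.3% in every normal-data cell, but the fix keeps the Mann-Whitney branch, which is itself sensitive to unequal spread. At ratio 2 with 30/20 or 35/15, that branch often accounts for more of the excess than the variance step.
- A reader might infer that the change is free. It nearly is at 30/20 or closer, but it costs power at 25/10 and 40/10, where the inflation is largest.
- A reader might infer that one fixed test should replace the normality check. That is a trade-off. At 25/25 with a shift of 0.6 SD, Welch throughout has 55% power against 62 to 63% for the plan's rule under skew (Gamma, shape 3), and about 64% against 78% under heavy tails (t, 3 df). A rank test throughout rejects in 7.0 to 8.9% of equal-mean normal datasets at 35/15, no better than the plan's rule.
- A reader might infer that the test is re-chosen at each flexion angle. The plan says only "Therefore, for all the continuous variables, the following tests will be used", which can equally mean one choice per variable. The missing detail is worth stating, but no error-rate consequence has been shown.

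**Conclusion.** The point holds as a modest, conditional defect. If size and spread both differ, choosing between Student's t and Welch by Bartlett and Levene moves the rule away from the declared 0.05: by about 1 to 2 points at 30/20, 1.5 to 3 at 35/15 and 3 to 5 at 40/10 when the smaller group is more variable, and downward when the larger group is. This rests on assumed splits, SD ratios of 1.5 to 2, normal data and preliminary tests at 0.05. If the groups are near-equal or the SDs equal, there is little to correct. The variance step causes only part of the drift; the rest comes from the normality check and its rank branch.

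**What to change.** Delete the Bartlett/Levene selection step. Use Welch for every parametric two-group comparison, report mean differences with 95% confidence intervals, and keep the two variance tests as diagnostics only. Welch is already on the plan's list, and with two groups Welch's ANOVA and Welch's t are the same test. This is a wording change, and it also removes the question of what to do when Bartlett and Levene disagree.

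Cost in power against the current rule, normal data and equal SDs: at most 0.3 points at 25/25, 17/16 and 30/20; 1.2 to 1.5 at 35/15; 2.0 to 2.7 at 25/10; 3.9 to 4.4 at 40/10 (for a shift of 0.8 SD, from 60.0–60.4% to 56.0–56.1%). With skewed or heavy-tailed data and equal SDs it is at most 1.8 points.

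Replacing the normality check is not part of this fix. If the check stays, state whether Shapiro-Wilk runs per group or on residuals, and whether the choice is made once per variable or at each angle. Which comparison the Welch test applies to depends on first reconciling the two cohorts in the analysis section with the three implant designs in the study population.
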